9.3 Physical Examination

A brief physical examination will be performed by a medically qualified professional at the Screening visit and Week 24. A review of the major body systems will be performed for example: skin, head/ears/eyes/nose/throat (HEENT), cardiovascular, pulmonary, abdomen, musculoskeletal, neurological, and gastrointestinal. Assessments of height (Screening visit only), weight, and vital signs (systolic and diastolic blood pressure, pulse, temperature, and respiration) are included and will be done at every visit.

9.4 Neurological Examination

This examination will be performed by a medically qualified professional and includes an assessment of cranial nerves, strength, coordination, reflexes, sensation, tremor and gait at screening and week 24 visits.

9.5 Electrocardiogram (ECG)

A standard 12-lead resting ECG will be performed at the screening and week 24 visits. The ECG report will be reviewed, signed, and dated by the investigator. Those with clinically significant ECG findings will be referred for follow-up as deemed appropriate by the investigator.

Excluded participants are patients who have either: 1) Screening ECG with QTc > 450 msec if male or QTc > 470 msec if female; or 2) A history of additional risk factors for Torsades de Pointes (TdP) (e.g., hypokalemia, family history of Long QT Syndrome) or are taking drugs that are known to cause QT-prolongation; Patients with a prolonged QTc interval in the setting of intraventricular conduction block (examples right bundle branch block [RBBB] or left bundle branch block [LBBB]), may be enrolled with sponsor approval; or 3) History of atrial fibrillation.

9.6 Orthostatic Vital Signs

Orthostatic vital signs are a series of vital signs of a patient taken while the patient is supine, then again while standing. Patient should be lying down for 3 minutes, and then take blood pressure and heart rate three times, 2 minutes apart each. Patient will be asked to stand for 3 minutes, and then blood pressure and heart rate will be taken again three times, 2 minutes apart each. Results will be recorded in the source document.

9.7 Clinical Laboratory Evaluation

Hematology, chemistry, liver function, B12, TSH levels and urinalysis will be collected at Screening and Week 24 visits. Laboratory samples to be tested consist of the following:

Hematology	Chemistry	Liver Function	Other Tests
Hemoglobin	Na	Albumin	TSH
Hematocrit	K	Total bilirubin	B12
RBC	Cl	Direct bilirubin	Urinalysis
Indices	CO2	Alkaline	
WBC	Glu	phosphatase	
Platelet count	BUN	Total Protein	
Differential count	Cr	AST - Aspartate	
	Ca	Transaminase	
		ALT -- Alanine	
		Transaminase	

Laboratory reports will be reviewed, signed and dated by the principal investigator. If any laboratory abnormalities have emerged in the course of the 24-week clinical trial, laboratory measures of that test will be repeated. The investigator will determine if abnormal values are clinically significant or not. If abnormalities persist, patients will be referred to their primary care physicians for treatment of the abnormality.

Quest Diagnostics and the Cleveland Clinic Laboratory will function as the research reference laboratories and will conduct all laboratory assessments.

9.8 Biomarker Studies and ApoE Genotyping

Serum biomarker measures will be collected for this study. They will include the following: Serum Aβ 40 and 42; sAPP-α, sAPP-β, Isoprostanes; Cytokines and other measures relevant to AD at Baseline and Week 24 visits. These assays will be done by the Genomics laboratory of the University of Nevada Las Vegas and Cleveland Clinic.

All participants will be asked to consent to the ApoE genotyping. DNA will be extracted from blood samples taken from participants and will be analyzed for ApoE genotype at the Baseline visit. This will permit secondary analyses of data on the impact of ApoE genotype on biomarkers of Alzheimer’s disease, clinical outcome measures and adverse events. ApoE genotyping will also be performed by the Genomics laboratory of the University of Nevada Las Vegas and Cleveland Clinic using established protocols.

9.9 MRI

A research grade (ADNI quality) MRI, acquired for each subject at the time of enrollment, will also be provided. T1, T2 and FLAIR or T2* sequence will be collected.

3D Sagittal T1 sequence: T1-weighted MPRAGE or MPRAGE-like sequence adhering to the Alzheimer’s disease Neuroimaging Initiative (ADNI) specifications. Typical scanner sequence parameters that could be used include:

Scanner	Sequence	Type	TR (ms)	TE (ms)	TI (ms)	NEX/NSA	Flip Angle(°)	Bandwidth
Siemens 3T	3D MPRAGE	(tfl)	2300	2.98	TI = 900	1	9	240 Hz/px
GE 3T	3D	IR-FSPGR	--	Min full	TI = 400	1	11	31.25 kHz
Philips 3T	3D	T1-TFE	Shortest	Shortest	TFE delay=900	1	9	Water-fat shift=1.8

All scans in this study will be evaluated using a stringent quality control procedure to ensure suitability for analysis. Quality control will be performed within 3 business days of image receipt so that in the event of an issue, the visit may be rescheduled if issues cannot be addressed through re-reconstruction. Quality control steps will include header checks, visual inspection, and quantitative inter-frame motion measurement. Image headers will be checked to ensure that the protocol was followed with regard to injected dose, injected volume, and start time after injection, number of frames, scan duration, and reconstruction parameters. Visual inspection will include checks for anatomical truncation (e.g., omission of lower slices of cerebellum), adequate image counts, and image noise such as streaking, image blur indicative of subject motion, asymmetry indicative of misalignment between emission and transmission scan, and other apparent artifacts. Quantitative motion measurement will involve calculation of the inter-timeframe translation and rotation, with preset thresholds above which a frame (or scan, if multiple frames) will not be accepted as suitable for analysis.

ADMdx has developed and will utilize an automated image processing pipeline, PETMAX™, which has secure user access, version control with back-up, and complete audit trail for use in clinical trials. PETMAX facilitates user interaction for visual inspection and quality control at multiple stages in the pipeline, and streamlines the execution of the many steps (including SPM functions) employed in image preparation and analysis. Results are logged and saved under version control.

9.10 [18F]-FDG-PET Imaging

There are two FDG-PET scans to be conducted per participant in this study. The scans will be done at the Screening visit for study eligibility, and at Week 24 visit for end of treatment scan and comparison.

The scanning protocol and equipment qualification requirements for this study will be consistent with those implemented in ADNI 2 (30). FDG-PET imaging data will be obtained at two sites: the Cleveland Clinic facilities in Cleveland, Ohio and Las Vegas, Nevada. Each of these sites uses a Siemens Biograph PET/CT LSO 16 slice camera. As part of site qualification, site practices will be reviewed, along with recent equipment calibration logs. If the site has a 3D-Hoffman phantom

scan collected within the past 12 months available, the scan will be provided for examination. If a de-identified patient brain scan can be made available, it will be provided for examination. The requirements for subject management in preparation for the scan, during FDG uptake, and during image acquisition will be reviewed with staff to ensure that these can be met. Since the Cleveland Clinic participates in ADNI as well as numerous other clinical trials, it is anticipated that requirements will be met.

The scanner will have an up-to-date calibration and normalization on the date of each imaging session. A daily QC check will be done at the beginning of the day the scanning will be completed. The scan will be visually inspected for abnormalities. If there is a possibility that the abnormality could impact the PET scan quality, the visit will be rescheduled.

Daily CT quality assurance will be performed as recommended by the specific vendor, and should typically include a "checkup/calibration" procedure and a water phantom scan. The checkup/calibration procedure guarantees optimum image quality by warming up the x-ray tube and should be performed at startup and within 1 hour prior to any scan. The water phantom provides quality measurements of 3 parameters. The parameters are the CRT value of water calculated in Hounsfield units (HU), the pixel noise of images calculated as a standard deviation, and the tube voltages measured directly on the x-ray tubes. These three measurements should be determined for all available kVp values.

Ideally, no hardware or software upgrades of the PET imaging system will occur during the study duration. If an upgrade needs to occur, ADMdx will be informed prior to the anticipated upgrade. Depending on the nature of the upgrade the site may be asked to repeat the phantom scans prior to scanning any additional subjects.

Quality control of blood glucose meter will be performed according to the manufacturer's or institution's procedure to ensure proper functioning. Quality control of dose calibrator will be performed throughout the course of the study. This typically will include daily constancy, quarterly linearity and annual accuracy.

9.11 ¹⁸F-AV-1451 Tau PET Imaging

At Screening visit, subjects who qualify for the study will come to the imaging center at a later date and will have a catheter placed for IV administration of ¹⁸F-AV-1451. Vital signs will be taken in a supine position immediately prior to administration of ¹⁸F-AV-1451 (within 30 minutes prior to injection) and at the completion of imaging prior to subject discharge. Subjects will receive up to a target dose of 370 mBq as a single IV bolus of ¹⁸F-AV-1451. A 20 minute dynamic image starting approximately 80 minutes post injection will be obtained. With sponsor approval sites may elect an alternative imaging protocol (i.e. different duration or start time) with additional time points.

All datasets will be submitted to AVID Radiopharmaceuticals for analysis.

Adverse events will be continuously monitored during the imaging session. Subjects who experience any adverse event will not be discharged until the event has resolved or stabilized.

The ¹⁸F-AV-1451 Tau PET imaging will also be performed within 30 days of Week 24/End of Treatment Visit.

Follow-Up Phone Call:

A follow-up phone call to the subject, or designated decision maker, will be conducted between 2 and 3 business days after ¹⁸F-AV-1451 imaging day, but not before 48 hours post-injection, to confirm subject wellbeing and to collect information about any new adverse events. If both of these days are not business days, the follow-up phone call can occur the following business day.

A companion protocol for the non-optional ¹⁸F-AV-1451 PET imaging study provides detailed information regarding the ¹⁸F-AV-1451 component and study procedures.

10. Potential Risks

10.1 Rasagiline Treatment Risk

The principal side effects observed in clinical trials in patients with PD include dyskinesia, nausea, falls, weight loss, constipation, postural hypertension, arthralgia, vomiting, abdominal pain, anorexia, and abnormal dreams.

Drug-drug interactions are historically a concern with MAO inhibitors, particularly tyramine-rich foods and beverages. Although such interactions have not been problematic in patients with selective MAO-B inhibitors, foods with particularly high concentrations of tyramine (aged cheese, sauerkraut, sausage, pickled herring) will be avoided in the course of the study. Similarly, sympathomimetic agents will also be avoided in trial participants.

The most significant drawback to the use of nonselective MAOIs is the risk of hypertensive emergencies, which can occur when a patient is exposed to sympathomimetic drugs, foods containing tyramine, or dopamine. By blocking the effects of MAO in the gastrointestinal tract, catecholamine concentrations are increased; and, in extreme cases, a hypertensive crisis can potentially result in a cerebrovascular accident or death.

The potential for tyramine interaction with rasagiline (doses tested, 0.5-2 mg) was assessed in 5 placebo-controlled clinical trials in healthy volunteers and PD patients. The results of the formal tyramine studies indicate that rasagiline can be used safely without dietary tyramine restriction at a dose of 1 mg/day. These data allowed removal of the dietary tyramine restriction from the rasagiline. This information was taken from the package insert of Azilect.

10.2 MRI Risk

The risks of MRI primarily arise from the possible introduction of ferromagnetic objects into a high magnetic field, which can create a dangerous projectile or lead to dysfunction or heating of an implanted medical device. All participants will be rigorously screened by MRI personnel to be certain that they do not have any medical contraindications for MRI, which include metallic foreign bodies in the brain or eye or cardiac pacemaker. There is a slight risk of anxiety due to claustrophobia. Any participant who experiences anxiety when placed into the MR scanner will be removed from the scanner, offered reassurance by the MR tech doing the scan, and offered the option of continuing or terminating the scan. If the participant decides that the anxiety associated with MRI is uncomfortable for them and they wish to terminate the scan, then the examination will be ended at that time. There will be no attempt to coerce participants to complete exams that they are uncomfortable with. Use of anxiolytic agents for completion of MRI scans is at the discretion of the principal investigator.

10.3 [18F]-FDG-PET Scan Risk

The primary risk related to PET is that of radiation exposure associated with the CT scan or transmission scan and the injected radiotracers. There is also minor risk associated with the venipuncture and radioisotope injection (pain and bruising or painful infiltration of a failed injection). The radiation dose is not expected to produce any harmful effects, although there is no known minimum level of radiation exposure considered to be totally free of the risk of causing genetic defects or cancer. The risk associated with the amount of radiation exposure participants receive in this study is considered low and comparable to everyday risks. No PET studies will be performed on pregnant or potentially pregnant women, as the protocol requires female subjects to be postmenopausal as a condition of participation.

10.4 CT Scan Risk

Subjects will also receive radiation of approximately 1 mSv from a “low dose” computed tomography (CT) acquired along with each PET scan. The low-dose CT will be used to align the position of the subject’s head for the PET image. The radiation dose from 1 combined PET/CT is about 8 mSv which is significantly less than the dose considered safe by the National Institute of Health (NIH) for research studies. However, this study will have 2 combined PET/CT scans during the study.

10.5 ¹⁸F-AV-1451 Tau PET Scan Risk

¹⁸F-AV-1451 will be administered IV up to a radioactive target dose of 370 MBq with a maximum human mass dose (MHD) limited to 20 µg of compound by weight. This dose is 150 fold lower than the NOAEL observed in the rat single dose toxicity study and is 50 fold lower than the NOAEL observed in the rat and dog repeat dose toxicity studies.

Human dosimetry has been obtained in nine subjects. The results estimated an Effective Dose of 8.92 mSv for an anticipated 370 MBq (10 mCi) injection and is comparable to the effective dose of approved 18F-labeled compounds such as FDG and florbetapir F 18 injection.

The proposed dose has been shown to be well tolerated and to have acceptable image quality in preliminary human studies.

10.6 Radiation Risk

One of the risks associated with radiation exposure is cancer. The natural incidence of getting cancer in the United States is about 40%. In this research study, including the companion protocol there will be four PET scans: FDG PET scan at Screening and at Week 24; and 18F-AV-1451 TAU PET scan at Screening and at Week 24. The annual radiation dose from the combined 2 FDG PET/CT scans is 16 mSv. The annual radiation dose from the combined 2 18F-AV-1451/CT scans is 19.84 mSv. The total radiation exposure for the four Pet Scans is 35.84 mSv. The maximum exposure allowed is 50 mSv per year.

10.7 Placebo Risk

Certain research participants in this study will receive a placebo. Taking a placebo may be similar to not taking any medication. Research participants who receive a placebo may have the disease stay the same or get worse, or the disease/condition may spontaneously get better just as it may have done without additional treatment.

10.8 Blood Draw Risk

The risks of blood draw include pain from the needle stick, bruising or infection at the site of venipuncture, or fainting as a response to blood draw.

11. STATISTICAL PLAN

11.1 Sample Size Determination

A study population of 25 subjects per arm (placebo, drug) has been estimated to be sufficient to detect a significant drug effect. Further, depending upon the effect size, a study population of 12 subjects per arm, assessed using an interim analysis, may also be sufficient to demonstrate effect. The number of subjects required to detect a significant change in regional cerebral glucose metabolism depends upon the drug action, patient variability within the regions affected, and the methods used to measure changes in glucose metabolism. For drugs causing a symptomatic effect, with or without additional disease-modifying properties, the N required is lower than that required to detect a modification to the rate of decline associated with disease. Specifically, we have modeled the number of subjects required to detect 5% and 10% increases in prefrontal cortex in mild to moderate AD patients using a region of interest approach, and have also confirmed estimates through review of published effect sizes from studies of donepezil, phenserine, and galantamine in AD patients.

11.2 Statistical Methods

Intent-to-Treat (ITT) - The primary FDG analysis will include all patients who received both a screening and end of study scan of acceptable quality. The primary clinical analysis will be a modified Intent-to-Treat (mITT) approach including all patients randomized and receiving at least one post-baseline assessment.

Per-Protocol (PP) population – All Intent-to-Treat subjects who complete the study (Week 24) and have ingested between 80% and 120% of the protocol prescribed study medication as measured by pill count.

Observed case – An observed case analysis of all patients completing the study will be conducted.

LOCF – Clinical data imputation will use the LOCF approach for missing patients

Responder analysis – Responders will be defined as those that have a significant improvement on brain metabolism on FDG for the whole brain or for any of the pre-specified regions.

A secondary analysis will compare the changes in FDG at 6 months compared to the projected expected metabolism based on the Baseline FDG findings.

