DIETARY ADJUSTMENT	
High tyramine-containing foods will be avoided:
 
 • Sausages, salami, pickled herring • Fava beans • Tap beers, non-pasteurized beers • Sauerkraut, yeast extract, soybean products including soy sauce • Aged cheeses
DRUG DOSAGE AND FORMULATION	
Subjects will take one 0.5 mg dosage Rasagiline tablet or the matching placebo once a day orally from Baseline visit to Week 4 visit. The dose will be titrated to one 1 mg dosage tablet or the matching placebo once a day starting on Week 5 through Week 24.

DURATION OF PARTICIPATION	
This is a 34-week study comprised of 7 in-clinic visits

PLACEBO	
A matching oral placebo will be used

ROUTE OF ADMINISTRATION	
Oral

PROCEDURES	
Physical and neurological exam, MRI, [18F]-FDG PET, ¹⁸F-AV-1451 Tau PET, ECG, vitals, clinical laboratory tests, MMSE, ADAS-Cog 11, CGIC, NPI, ADCS-ADL, Digit Span, COWAT, QoL-AD/Study Partner

STATISTICAL CONSIDERATION	
Intent-to-Treat (ITT) - The primary FDG analysis will include all patients who received both a screening and end of study scan of acceptable quality.
 
Modified Intent-to-Treat (mITT) – All randomized subjects who have been dispensed study medication and have one post-baseline visit during the blinded phase of the study.
 
Per-protocol (PP) population – All ITT subjects who complete the study (Week 24) and have ingested between 80% to 120% of the prescribed study medication as measured by pill count.
 
Observed case – An observed case analysis of all patients completing the study will be conducted.
 
Last Observation Carried Forward (LOCF) – Clinical data imputation will use the LOCF approach for missing patients.
 
Responder analysis – Responders will be defined as those that have a significant improvement on brain metabolism on FDG for the whole brain or for any of the pre-specified regions.
 
A secondary analysis will compare the changes in FDG at 24 weeks compared to the projected expected metabolism based on the Baseline FDG findings.

ADVERSE EVENTS	
SAFETY
 
Orthostatic vital signs, ECG, hematology, chemistry, TSH, B12 and urinalysis (UA) collected at Screening and at end of study

	
TOLERABILITY
 
Side effects data will be collected and converted to systems data using a data dictionary.
 
DSMB No Independent DSMB is required.

--	--

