3.2 Secondary Objectives

- To evaluate the efficacy of Rasagiline 1 mg once daily compared to placebo after 24 week treatment on cognition (ADAS-cog), activities of daily living (ADCS-ADL), global function (CIBIC+), and neuropsychiatric symptoms (NPI)
- To evaluate the efficacy of Rasagiline 1 mg once daily compared to placebo after 24 week treatment on measures of executive function (mazes and cancellation of the ADAS-Cog13, Digit Span test, and Controlled Oral Word Association Test [COWAT] for verbal fluency)
- To evaluate the safety and tolerability of Rasagiline as measured by incidence of adverse events/serious adverse events (AEs/SAEs) clinical lab test data, vital signs, 12 lead EKG data, brain MRI finding

4 Populations of Interest

- Intent-to-Treat (ITT) Population: All consented randomized subjects grouped according to the treatment assigned at randomization, regardless of any protocol violations or any crossovers.
- Per-Protocol (PP) Populations: All Intent-to-Treat subjects who meet the inclusion criteria and exclusion criteria specified for enrollment in the protocol, and complete the study (week 24), have ingested between 80% and 120% of the protocol prescribed study medication as measured by pill count, and with no protocol violations that affect the analysis.

5 Analyses Populations: Definitions

- FDG Analyses: The primary FDG analysis will include all patients who received both a screening and end of study scan of acceptable quality.
- Clinical Outcome Analyses: The primary clinical analyses will include the ITT population.
- Safety Analyses: The primary clinical analyses will include the ITT population.
- Responder analysis: Responders will be defined as those that have a significant improvement on brain metabolism on FDG for the whole brain or for any of the pre-specified regions.

6 Enrollment and Participant Flow

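### The Protocol labels the primary FDG set Intent-to-Treat although entry requires a usable second scan, and neither document plans an analysis of missing second scans

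*Protocol*

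**What the plan says.** **Primary FDG population.** Protocol 11.2 and the Synopsis (Statistical Consideration) say: "Intent-to-Treat (ITT) - The primary FDG analysis will include all patients who received both a screening and end of study scan" of acceptable quality. SAP section 5 keeps the same two-scan rule but lists it under FDG analyses. SAP section 4 defines ITT as: "All consented randomized subjects grouped according to the treatment assigned at randomization, regardless of any protocol violations or any crossovers". The Protocol's Per-Protocol set is built on its own ITT label (Synopsis: "All ITT subjects who complete the study (Week 24", plus an adherence range).

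**Scan schedule.** Protocol 9.10: "There are two FDG-PET scans to be conducted per participant in this study", one at Screening and one at Week 24. Protocol 5.4 asks patients who withdraw to complete Visit 6. The Visit 6 list (7.6), Table 2 and Appendix B show no FDG PET at that visit. Protocol 5.5 says withdrawn patients will be followed and will not be replaced.

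**Missing data.** Protocol 11.2: "Clinical data imputation will use the LOCF approach for missing patients". It also says "An observed case analysis of all patients completing the study will be conducted". Nothing is said about missing FDG values. The FDG methods are t-tests by region, NPAIRS and SPM contrasts (Protocol 11.4.3-11.4.4, SAP 8.3-8.4).

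**Clinical outcomes.** Protocol 11.2 uses a modified ITT set needing at least one post-baseline assessment, with LOCF. SAP section 5 says: "Clinical Outcome Analyses: The primary clinical analyses will include the ITT population". SAP section 9 fits a linear mixed model (GEE for the CGIC).

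**Discontinuation.** SAP 6.2 and 6.3 report numbers and reasons by arm and compare proportions by Fisher's exact test.

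**The concern.** An ITT label tells a reader that the comparison is protected by randomisation. Here it is protected only if having a usable second scan is unrelated to arm and outcome, or related to outcome in the same way in both arms. If patients on one arm leave more often, or leave for reasons tied to metabolic decline, the two-scan comparison can shift with no true drug effect. The discontinuation tables would show that patients left, not how far the FDG result moved.

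Two features make the gap structural. The visit assigned to early leavers carries no FDG scan, so their endpoint is missing by schedule. And the only imputation rule in either document covers clinical data.

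For the clinical outcomes the stake is different. Two populations and two methods are on record and can give different answers, so one must be fixed in advance.

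**Working it through.** **1. The Protocol's own figures.** Protocol 11.3 gives three scenarios (two-sided 0.05) but no SD. Back-solving with a two-sample t-test:

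| Scenario | Implied SD (% of mean) |
|---|---|
| 5% difference, 26 per arm, 70% power | 7.12 |
| 5% difference, 32 per arm, 80% power | 7.03 |
| 10% difference, 8 per arm, 80% power | 6.64 |

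The scenarios agree on an SD of 6.6-7.1%. This checks consistency; it does not reproduce the figures independently. The text reads as the spread of SUVr levels. The SD of change is SD of level × √(2(1−r)), with r the Screening-to-Week 24 correlation. At r = 0.5 the two SDs are equal; at r = 0.8, 7.1 × √0.4 = 4.5. The documents do not give r.

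**2. Power for a 5% difference (t-test).** The enrolled number is 25 per arm; the loss rate is assumed, because the documents give none.

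| SD of change | 25 per arm | 22.5 (10% loss) | 20 (20% loss) |
|---|---|---|---|
| 7.12 | 68% | 63% | 58% |
| 7.03 | 69% | 65% | 59% |
| 6.64 | 74% | 70% | 64% |
| 4.5 | 97% | 95% | 93% |

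**3. Bias with no true effect.** Let leavers change by g points less than stayers. If both arms share the same overall mean m, stayers in an arm with loss p average m + p·g. The bias in the two-scan comparison is therefore (p_A − p_B) × g.

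- 30% vs 10% loss, g = 2 to 5: 0.20 × 2 = 0.4 to 0.20 × 5 = 1.0 points.
- 20% vs 10% loss: 0.10 × 2 = 0.2 to 0.10 × 5 = 0.5 points.
- Equal loss, same g: 0.0 points.

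**4. Type I error for one region.** From 200,000 simulated trials per case: 25 per arm, random number of leavers, pooled t-test, g = 2 to 5.

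| Loss by arm | SD 7.1 | SD 4.5 |
|---|---|---|
| 30% vs 10% | 5.4-7.2% | 5.8-10.4% |
| 20% vs 10% | 5.1-5.6% | 5.3-6.5% |
| 20% vs 20%, equally informative | 5.0% | 5.0% |

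Hand check of the 30% vs 10% case, g = 5, SD 7.1. Expected scans are 17.5 and 22.5, so SE = 7.1 × √(1/17.5 + 1/22.5) = 2.26. Bias/SE = 1.0/2.26 = 0.44. The normal tail areas beyond ±1.96 after that shift sum to 7.3%, which agrees with the simulation.

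**5. Clinical outcomes, side by side.**

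| | Protocol 11.2 | SAP 4, 5 and 9 |
|---|---|---|
| Population | Randomised with at least one post-baseline assessment | All randomised |
| Method | LOCF for missing data | Mixed model over 24 weeks (GEE for the CGIC) |

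**The case against.** **The set may suit the question.** The primary objective concerns exposure to 1 mg daily, Protocol 9.10 calls the second scan an end-of-treatment scan, and this is a small proof-of-concept trial. That stands as a reason to keep the two-scan set as primary. It is no reason to call it ITT, or to leave its missing members unexamined.

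**The membership rule is open, and the SAP labels it properly.** True. The labelling error lies in the Protocol, and the repair is mostly wording.

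**Harm is conditional.** This also stands. Loss rates, imbalance, the leaver gap and r are all assumed. The 10.4% figure needs 30% vs 10% loss, r of 0.8 and a gap as large as the whole 5% effect modelled in Protocol 11.3. Nothing in the documents makes that combination likely.

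**Stronger readings the documents do not support.**

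- A reader might infer that the Per-Protocol and observed-case sets are further FDG analyses that all depend on completing. Protocol 11.2 does not say they apply to FDG, and the only repeat in the Per-Protocol set that the SAP states is for clinical measures (section 9).
- A reader might infer that LOCF would give early leavers zero change on MMSE and QoL-AD, which have no scheduled post-baseline value before Week 24. That needs baseline to be carried forward, which neither document states.
- A reader might infer that the primary result will be biased. With balanced, equally informative loss it is not, under no true effect.
- A reader might infer that scanning early leavers at Week 24 is plainly better. It changes the estimand and can lower power (see the fix).

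**Conclusion.** The point holds as a gap in labelling and missing-data planning that should be fixed; it does not show that the primary result will be wrong. Three things rest on the text alone: the Protocol's ITT label conflicts with the SAP's definition, early leavers have no scheduled Week 24 FDG value, and neither document plans an FDG analysis that tests their absence. The conflict between LOCF in a modified ITT set and a mixed model in all randomised patients is also textual.

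The size rests on assumptions. With equal, equally informative loss of 20%, the cost is about 10 points of power for a 5% difference (68-69% to 58-59%, SD 7.0-7.1%) and no inflation of type I error. Inflation is slight at 20% vs 10% loss and becomes material only when loss is clearly unbalanced and strongly tied to outcome.

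**What to change.** 1. **Rename the set.** In the Synopsis and Protocol 11.2: *FDG-evaluable set: all randomised patients with a screening and a Week 24 FDG scan of acceptable quality, analysed as randomised.* Keep ITT for all randomised patients, as in SAP section 4, and rebase the Protocol's Per-Protocol definition to match.
2. **Add a sensitivity analysis to SAP 8.4** of the between-arm SUVr change in all randomised patients. Impute within arm from a small pre-specified model (screening SUVr, AD Progression score, one named clinical score). Then shift the imputed active-arm changes from 0 to −5 percentage points and report where the conclusion changes. Name one reference region in advance, since SAP 8.4 lists three and permits another. Report missing second scans by arm and reason.
3. **Settle the clinical analysis.** Strike LOCF from the Synopsis and Protocol 11.2, use the SAP's mixed model on all observed data, and state one clinical population in both documents.
4. **Reconcile Protocol 5.4, 5.5, 6.4, 7.6 and 9.2 with SAP 6.3**, so that stopping study drug and leaving data collection are recorded separately. No view is taken on the treatment rule.

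**Cost.** Document wording and a little more analysis work. With about 20 complete cases per arm the imputation will be imprecise, which is why the model must be small and the shift analysis should carry the interpretation.

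**Optional, for the sponsor to decide.** Obtain the already planned second scan at Week 24 from consenting early leavers. If 20% of active-arm scans were off drug with no effect retained, a 5-point difference becomes 0.8 × 5 = 4.0. Power with 25 per arm is then 49-51% (SD 7.0-7.1%), against 58-59% for 20 completers per arm. With half the effect retained (4.5 points) it is 59-60%. The gain is less bias, not more power. If adopted, Protocol 9.10 must also change, because it describes the scan as end of treatment, and an on-drug FDG analysis must be specified.
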